Domain 4 (exploratory outcomes: HIV/PrEP linkage outcomes): (a) number of HIV+ youth referred to HIV treatment at 3, 6, and 12 months FUs, (b) number of HIV+ youth attending at least one treatment appointment at 3, 6, and 12 months FUs; (c) number of youth behaviorally PrEP eligible referred to PrEP/medical care at 3, 6, and 12 months FUs, (b) number of youth behaviorally PrEP eligible attending at least one HIV care appointment care at 3, 6, and 12 months FUs.

TRIAL MANAGEMENT

Study/data collection sites

Data will be collected at **Brooklyn Justice Initiative (BJI), run by Center for Court Innovation**. BJI is an alternative sentencing program (ASP) for JIY processed through Brooklyn Criminal Court. BJI aims to reduce re-offending and increase public safety; promote use of meaningful social services; provide rigorous compliance monitoring; and reduce criminal convictions and use of jail. Located in the Brooklyn Criminal Courthouse, BJI serves 9,000 youth/year; almost all (94%) are mandated to BJI for ≤ 15 days.

Study sample description

To address the study aims we will collect data from a sample of youth aged 18-24 who have been placed in BJI (sample 1), from a sample of HIV testing outreach staff (sample 2) and from staff at BJI (Sample 3).

Sample size and power

The total sample size of sample 1 will comprise N=472 youth currently enrolled at BJI: n=14 youth will serve on an advisory panel to provide feedback as MOVE and NYSBIRT are adapted; n=8 youth will pilot test the adapted Link2CARE protocols prior to the efficacy test of Link2CARE; and n=450 youth will be randomly assigned (1:1) to either Link2CARE or standard of care. Sample 2 will comprise N=2 Project STAY outreach workers who will be embedded at BJI and will deliver all elements of Link2CARE to youth. Sample 3 sample size is expected to be all 15 staff who work at BJI.

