	Youth n=450	1) Between 18-24 years of age 2) Currently enrolled in BJI 3) Engaged in any unprotected sexual activity (lifetime), 4) Conversant in English (in the past two years, only two JIY at BJI have required language assistance).	1) Medical or psychiatric illness requiring hospitalization 2) Serious suicidal or homicidal ideation 3) HIV+ status by self-report and linked to care
	Project STAY staff n=2	1) Currently employed Project STAY and involved in delivering Link2CARE.	None
	BJI staff n=15	1) Currently employed at BJI	None

Target population distribution

Inclusion of Women. There is no inclusion or exclusion of participants based on gender. Based on demographic data from the Brooklyn Justice Initiative, we anticipate females will comprise 28% of the youth sample, representing the demographics of the justice system nationwide.

Inclusion of Minorities. We will not exclude participants based on ethnicity. The majority of youth enrolled in the Brooklyn Justice Initiative are minority (56% African American, 18% Hispanic), representing the demographics of the justice system nationwide.

Children: The proposed study does not include children aged 18 or younger. The application proposes to develop a screening, brief intervention and linkage-to-care service delivery model that targets those at significant risk for HIV and SU. In the US, youth age 18-24 carry the burden of HIV and substance use problems compared to youth younger than 18. Moreover, the development of a linkage-to-care program for youth younger than 18 would have to involve caregivers who can provide consent for youth to receive both SU and HIV treatment. Involvement of caregivers would necessitate a different linkage-to-care intervention, which is beyond the scope of the proposed study.

Project Timeline

TABLE 2: Projected Timetable

Months	Year 1		Year 2		Year 3		Year 4		Year 5	
	1 – 6	7 – 12	13 – 18	19 – 24	25 – 30	31 – 36	37 – 42	43 – 48	49 – 54	54 – 60
Adaptation and pilot testing of MOVE and NSYBIRT	■	■								
Train staff			■							
Recruit JIY			■	■	■	■				
Implement Link2CARE			■	■	■	■	■			
JIY assessment (3-month)				■	■	■	■			
JIY assessment (6-month)				■	■	■	■	■		
JIY assessment (12-month; main outcomes)					■	■	■	■	■	
Staff assessments (implementation outcomes)		■			■		■			

Acknowledgment permission requirement

The PIs acknowledge the requirement to request and receive permission from the PO for protocol or DSMP changes in advance of their implementation.

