DATA MANAGEMENT AND ANALYSIS

Data acquisition, entry and transmission

Study data will be collected in Phases 1 and 2. All Phase 1 and all baseline assessments (Phase 2) will be collected at BJI. Subsequent Phase 2 assessments will occur at BJI, in the participant’s home or at another agreed upon location. Note: BJI is not involved in survey administration, data entry and management, or data storage.

Phase 1: Advisory Panel data: Peer (n=14) and Staff (n=6) Advisory Panels will meet in a series of Panel workgroups during Phase 1 to provide feedback on the adaption of the SU and HIV interventions. Data from these Panel workgroups will be gathered in note form by work group facilitators and will not contain any participant identifying information. These data will be transcribed by research assistants and will be used between workgroups to inform adaptation of interventions.

Pilot data: n=8 youth who participate in a pilot of the SU and HIV protocols will complete paper-and-pencil process measures following the completion of the pilot which will be administered by human subject-trained research assistants (RAs). These research assistants will bring completed questionnaires to the research offices at NYSPI on the day of data collection. These data will be entered in an electronic database by human subject-trained research assistants. This database will be stored on password-protected computers in encrypted files. Researchers will retain the pilot process assessments until the completion of all project activities in Year Five when they will be destroyed following HIPAA standard document destruction services.

Phase 2: Substance use and HIV behavioral risk screen. Following randomization and baseline assessments, n=225 JIY randomized to Link2CARE will complete substance use and HIV behavioral risk screeners. Screening will take place at BJI in private rooms or other agreed upon location (for follow-up survey assessments). Data will be captured on encrypted, password protected computers, entered directly by human subjects-trained RA's into CiW using Sawtooth Software. Sawtooth Software allows for all standard question types, skip patterns, and data piping. Web-based data collection will **not** be used. Following interview completion, RAs will then transport interview data to NYSPI in the encrypted password protected computer, and immediately upload it upon return into the master database at NYSPI held on a secure server.

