compared to the standard of care; all hypothesis tests will be conducted under the control of familywise error rate no greater than 0.05 level. The Holm step down procedure will be employed to adjust for multiple comparisons.

1. **Domain 1 (primary outcomes: HIV outcomes):** (a) total number of unprotected anal and vaginal sex occasions in past three months at 12 month FU; (b) acceptance of HIV testing at initial offering (y/n), (c) any HIV testing between 6-month and 12-month FU (y/n).
2. **Domain 2 (SU outcomes):** (a) frequency of youth substance use in past 30 days at 3-, 6- and 12-month FUs; (b) number of youth referred to SU treatment at 3-, 6- and 12-month FUs; at (c) number of youth attending intake plus one treatment session at 3-, 6- and 12-month FUs.
3. **Domain 3 (exploratory outcomes: HIV/PrEP linkage outcomes):** (a) number of HIV+ youth referred to HIV treatment at 3, 6, and 12 months FUs, (b) number of HIV+ youth attending at least one treatment appointment at 3, 6, and 12 months FUs; (c) number of youth behaviorally PrEP eligible referred to PrEP/medical care at 3, 6, and 12 months FUs, (b) number of youth behaviorally PrEP eligible attending at least one HIV care appointment care at 3, 6, and 12 months FUs.
4. **Domain 4 (STI testing outcomes):** a) acceptance of STI testing at initial offering (y/n), (b) any STI testing between 6-month and 12-month follow up; (c) number of STI+ youth referred to STI treatment at 3, 6, and 12 months FUs; (d) number of STI+ youth attending ≥ 1 treatment appointment at 3, 6, 12 months FUs.

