Analysis plan for Specific Aims 2 and 3. Descriptive statistics will be computed to quantify implementation at every step, by participant and by provider. Thus, we will be able to compute uptake of LINK2CARE, dose/intensity of intervention received, number of providers delivering each intervention, and other implementation parameters. Of note for Aim 2, which seeks to examine the proposed mechanisms of change of the intervention on HIV, STI and substance use outcomes, a given outcome (e.g. HIV/STI testing uptake, or PrEP uptake or reduced substance use) of this analysis will only be examined among those for whom it is relevant. For example, if a youth does not meet criteria for PrEP and as such is not offered PrEP, we would not include this youth in analyses of mechanisms of change of Link2CARE as they influence substance use or PrEP uptake as an outcome. We will examine the changes in specific outcomes (e.g. sexual behavior post-intervention) as a function of proposed theory-based intervention mediators (e.g. predisposing characteristics, enabling resources, perceived need for treatment/services). We will use structural equation models for these analyses. Structural equation modeling is preferred to multiple regression techniques because of the potential measurement error in our mediating variables and because of the possible feedback between dependent and mediating variables. We will test the model described in Figure 1 in the application, entering intervention condition as exogenous variables and the mediating factors included in Figure 1 as endogenous variables. Prior to conducting the structural analyses, however, we will examine the effects of the intervention on the putative mediating variables; a condition for inclusion in the equation will be a significant intervention effect on the potential mediators. Using standardized path coefficients, we will examine the relative associations of mediators to behavior change. We will also examine the path coefficient for the direct effect of the intervention after removing the effects of mediating constructs. For example, Link2CARE may have a more positive effect on acceptance of HIV (and STI) testing among JIY with greater perceived HIV risk, greater motivation to receive services, or positive HIV-testing history. Similarly, Link2CARE may have more positive effect on linkage outcomes when operating in an ASP that is more supportive of concepts perceived as innovative by both BIJ and STAY staff. Here, organizational culture would appear to modify Link2CARE's impact on youth service referral and engagement outcomes. We will examine the Lagrange Multiplier and Wald Tests to consider the deletion or inclusion of paths⁵; ultimately, however, deletion or inclusion of paths will be informed by theoretical underpinnings. Once the model is identified, we will test for group differences between intervention conditions in latent constructs and in the proposed paths between these constructs. This method will allow us to estimate the intervention effects on the constructs directly as well as their relationships to one another.⁶ We will use three goodness-of-fit indices: Bentler-Bonnet's Normed Fit Index, Bentler-Bonnet's Non-Normed Fit Index, and the Comparative Fit Index. We will also verify the root mean-square error of approximation (RMSEA) as an index of misfit. Well-fitting models will have fit indices of .90 or higher and $< .06$ for RMSEA.

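### The worked example for Aim 2 uses PrEP ineligibility to exclude youth from the substance-use mechanism analyses, against the section's own rule of relevance to the outcome

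*Combined protocol and SAP*

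**What the plan says.** The section 'Analysis plan for Specific Aims 2 and 3' sets an inclusion rule for the mechanism analyses: a given outcome "will only be examined among those for whom it is relevant". It names testing uptake, PrEP uptake and reduced substance use as separate examples of such outcomes.

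The next sentence illustrates the rule. The case described is "if a youth does not meet criteria for PrEP and as such is not offered PrEP", and the consequence is "we would not include this youth in analyses of mechanisms of change of Link2CARE as they influence substance use or PrEP uptake as an outcome". No substance-use criterion appears in the example.

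The same section makes a statistically significant intervention effect on a candidate mediator a condition for that mediator to enter the structural equation model.

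Two other places bear on the point:

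- Under 'Data acquisition, entry and transmission', the Phase 2 screening paragraph says that, after randomisation and baseline assessment, "n=225 JIY randomized to Link2CARE will complete substance use and HIV behavioral risk screeners". No equivalent screen is described for standard of care (SOC).
- The paragraph on youth survey interviews says that all 450 youth are interviewed at baseline, 3, 6 and 12 months.

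**The concern.** The example does not follow from the rule. Whether a youth meets PrEP criteria decides whether PrEP uptake is a meaningful outcome for that youth. The document gives no reason why it should also decide whether substance use is. An analyst who follows the example drops randomised youth from the substance-use models on a criterion never tied to that outcome. An analyst who follows the rule departs from the example.

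Two things are at stake. First, the mediator entry condition is a comparison between arms, so a smaller sample makes it more likely that a real mediator is screened out. Second, Aim 1 would describe substance use in all randomised youth while Aim 2 explained it only in the PrEP-eligible, with no stated reason for the difference.

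A connected gap is that the plan does not define behavioural PrEP eligibility or say how it is established in SOC. If it were taken from the screener described only for Link2CARE, the filter would work differently in the two arms.

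**Working it through.** **Text comparison.** The rule is specific to the outcome. In the example the trigger is PrEP criteria alone, and the exclusion covers two outcomes, substance use and PrEP uptake. The substance-use outcomes in 'Study aims and primary and secondary outcomes' and in the Aim 1 analysis plan carry no PrEP restriction. No other section overrides the example.

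**Inputs**

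- Randomised: "n=450 youth will be randomly assigned (1:1) to either Link2CARE or standard of care" ('Sample size and power').
- 25% attrition, 338 completers, 169 per arm, effect 0.35 SD, 80% power, Bonferroni over three outcomes (same section).
- Two-sided critical value 2.3940 for 0.05/3 ('Trial Stopping Rules').
- PrEP-eligible share s: not given. Assumed range 25% to 90%, equal in both arms.

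**Reproducing the plan's own figure**

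- Completers: 450 × 0.75 = 337.5, i.e. 338.
- n per arm = 2 × (2.394 + 0.842)² / 0.35² = 171, against 169 stated.
- Power at 169 per arm = Φ(0.35 × √(169/2) − 2.394) = Φ(0.823) = 79.5%, against 80% stated.
- Detectable effect = (2.394 + 0.842) × √(2/n): 0.365 at 30% attrition (n = 157.5; stated .36) and 0.319 with 100 more participants (n = 206.25; stated .32).

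The plan's figures reproduce, so the same formula can be used for the restricted sample. The plan states no power for Aim 2.

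**Effect of the exclusion.** n per arm = 169 × s; power = Φ(0.35 × √(n/2) − z), with z = 1.960 or 2.394; detectable effect at 80% power = (z + 0.842) × √(2/n).

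| Assumed share s | Completers kept | Power, 0.05 | Detectable SD, 0.05 | Power, 0.05/3 | Detectable SD, 0.05/3 |
|---|---|---|---|---|---|
| 100% (no exclusion) | 338 | 89.6% | 0.305 | 79.5% | 0.352 |
| 90% | 304 | 86.3% | 0.321 | 74.5% | 0.371 |
| 75% | 254 | 79.6% | 0.352 | 65.3% | 0.406 |
| 50% | 169 | 62.4% | 0.431 | 45.3% | 0.498 |
| 25% | 84 | 36.3% | 0.610 | 21.6% | 0.704 |

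**When would power halve?** At 0.05, half of 89.6% is 44.8%, so 0.35 × √(n/2) = 1.960 − 0.131 = 1.829. That gives n = 54.6 per arm and s = 54.6/169 = 32%. At 0.05/3, half of 79.5% is 39.7%, so 0.35 × √(n/2) = 2.394 − 0.260 = 2.134. That gives n = 74.4 and s = 44%.

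**Limits.** These are powers for a two-group mean difference. They are a fair guide to the mediator entry condition, which compares arms, but not to the power of the structural equation model. The 0.35 SD is borrowed from the primary-outcome calculation. The 338 is an upper bound, because the plan does not say for what share of youth substance use is itself relevant.

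**The case against.** The strongest reply is that this is a drafting slip. The governing rule is sound, the faulty sentence is only an example, and it reads as if two illustrations had been merged. A sensible analyst would apply the rule. That is plausible, but this is the only place where the plan shows how an Aim 2 population is chosen, and nothing elsewhere corrects it.

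A reader might infer that the example discards most of the sample or most of the power. The documents do not support that. They give no eligible share, and the entry criterion in Table 1, "Engaged in any unprotected sexual activity (lifetime", does not fix one. At 90% eligible, 304 of 338 completers remain and power at 0.05/3 falls only from 79.5% to 74.5%. More than half the sample is lost only if fewer than half are eligible.

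A reader might also infer that the exclusion breaks randomisation by setting a selected Link2CARE group against unselected SOC youth. That is not established either. No section says that PrEP eligibility comes from the Link2CARE-only screener. The baseline interview is given to both arms, and the plan compares arms on outcomes such as "number of youth behaviorally PrEP eligible referred to PrEP/medical care at 3, 6, and 12 months FUs", which implies that eligibility is known in both. A filter on having been offered PrEP would also remove SOC youth who had no offer, not keep them unselected. What remains is that the source of eligibility in SOC is unstated, and an arm-specific source would be a problem.

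**Conclusion.** The point holds as a contradiction between the Aim 2 rule and its example. Followed as written, the example drops youth from the substance-use mechanism analyses on a criterion the document never connects to substance use.

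The size is conditional on the unstated eligible share and could be small or large, as the table shows. It rests on a two-group approximation, an effect of 0.35 SD, 338 completers and an equal eligible share in both arms. The risk to comparability between arms is conditional too: it arises only if eligibility is taken from information collected differently by arm.

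The scope is Aim 2 alone; the Aim 1 analyses, including those of substance use, are untouched. The example should be corrected before the mechanism analyses are run, but the error does not threaten the primary result.

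**What to change.** 1. Delete 'substance use or' from the example, so that PrEP eligibility restricts only the PrEP outcomes.
2. If the substance-use mechanism analysis is to be restricted at all under the relevance rule, define the subset by baseline substance use, measured the same way in both arms, and state the expected number.
3. For the PrEP analyses, state that eligibility is set from information collected identically in both arms, for example the baseline interview given to all 450, and not from the post-randomisation screener described only for Link2CARE.

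The first change costs one edit. The second and third need a sentence or two each. No new data are needed if the baseline interview holds the required items. The document does not list those items, so this should be checked. These changes concern who enters an analysis, not who is offered PrEP.

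### Admitting mediators to the Aim 2 model only when the intervention effect on them is significant biases the split between indirect and direct effects; the size depends on mediator effects the plan does not give

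*Combined protocol and SAP*

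**What the plan says.** The rule is in the section Analysis plan for Specific Aims 2 and 3. Candidates are described as "proposed theory-based intervention mediators (e.g. predisposing characteristics, enabling resources, perceived need for treatment/services" and so on; the full list is in a figure of the grant application, which is not part of these documents. The order of work is:

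1. Screen: "Prior to conducting the structural analyses, however, we will examine the effects of the intervention on the putative mediating variables", with the rule that "a condition for inclusion in the equation will be a significant intervention effect on the potential mediators". No significance level is given for the screen and no separate data set is named.
2. Compare the mediators: "Using standardized path coefficients, we will examine the relative associations of mediators to behavior change".
3. Read off the remainder: "We will also examine the path coefficient for the direct effect of the intervention after removing the effects of mediating constructs".

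Each outcome in this analysis "will only be examined among those for whom it is relevant", so the sample can be smaller than for Aim 1. The section gives no power for mediator effects, no test or interval for an indirect effect, no allowance for selection, and no sensitivity model that keeps every mediator.

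**The concern.** A significance screen followed by estimation in the same data has two effects. A mediator that passes does so partly because its estimated intervention effect was high by chance, so the retained path is too large on average. A true mediator that narrowly fails is treated as if it carried nothing, and what it carries passes to the direct path or, where mediators are correlated, to the retained mediators.

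Aim 2 asks through which mechanisms Link2CARE works. The retained paths and the remaining direct effect are its answer. An intervention that works through its hypothesised mechanisms could look as if it worked partly by some unexplained route, or through one mediator more than it does.

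**Working it through.** **Inputs from the documents.** 169 completers per arm (Sample size and power) and two-sided testing (Trial Stopping Rules).

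**Assumptions, because the documents are silent.** Three true mediators, each with intervention effect *a* in SD units; mediator-to-outcome path *b* = 0.3; true direct effect zero; linear models; mediators observed without error; screen at two-sided 0.05.

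**The plan's own figure.** No figure is stated for mediation. The Aim 1 statement is 80% power at 0.35 SD with Bonferroni over three outcomes. Check: 0.35 × √(169/2) = 3.217; 3.217 − 2.394 = 0.823; Φ(0.823) = 0.795. It reproduces, and it is used here only to fix the sample size.

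**Step 1: the screen.** SE = √(2/169) = 0.1088. A mediator passes only if its estimate exceeds 1.96 × 0.1088 = 0.213 SD in absolute value.

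**Step 2: inflation of the retained intervention-to-mediator path.** This is the truncated-normal mean. At *a* = 0.20, (0.213 − 0.20)/0.1088 = 0.12, so P(pass) = 0.452. The mean estimate given a pass is 0.20 + 0.1088 × φ(0.12)/0.452 = 0.295, and 0.295/0.20 = 1.48.

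**Step 3: share relabelled, uncorrelated mediators.** Dropped mediators count as zero, so the share is 1 − P(pass) × (mean given pass)/*a*. At 0.20: 1 − 0.452 × 0.295/0.20 = 0.33. The mediated effect is 3 × 0.20 × 0.3 = 0.180, so about 0.060 appears as direct.

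**Step 4: correlated mediators.** These shares come from simulation, 4,000 runs per setting.

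| *a* (SD) | P(pass) | Mean given pass | Ratio to truth | Share relabelled, formula | Simulated, correlation 0 / 0.3 / 0.5 |
|---|---|---|---|---|---|
| 0.15 | 0.281 | 0.280 | 1.87 | 48% | 46% / 32% / 29% |
| 0.20 | 0.452 | 0.295 | 1.48 | 33% | 33% / 17% / 12% |
| 0.30 | 0.787 | 0.340 | 1.13 | 11% | 11% / 4% / 2% |
| 0.35 | 0.896 | 0.372 | 1.06 | 5% | 5% / 1% / 0% |

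At 0.50 SD, P(pass) is 0.996 and both effects vanish. Simulation error is one to two percentage points: at 0.20 SD, 0.116/√4000 = 0.0018, and 0.0018/0.180 = 1.0 point. A 20,000-run simulation at 0.20 SD gave direct effects of 0.061, 0.035 and 0.026 at correlations 0, 0.3 and 0.5, that is 34%, 19% and 14% of 0.180.

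**Step 5: the mediator-to-outcome path.** At 0.20 SD the mean retained path is 0.300 with uncorrelated mediators, so it is unbiased. It is 0.372 at correlation 0.3 and 0.393 at 0.5, because retained mediators absorb dropped ones.

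**Step 6: against sampling error.** The standard error of the direct effect is about 0.12, so a shift of 0.06 is 0.06/0.12 = half a standard error. With a true direct effect of zero, the screened model declared it significant in 7–8% of runs at 0.15–0.20 SD with uncorrelated mediators, and in about 5% with correlated ones.

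**Step 7: the full model.** With all three mediators kept at 0.20 SD, the mean indirect effect is 0.180 and the mean direct effect 0.000. The SD of the direct-effect estimate is 0.109, against 0.116 for the screened model.

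**Sensitivity.** At 0.20 SD with uncorrelated mediators, an assumed 85 per arm in a subset gives 26% passing, a ratio of 1.96 and 50% relabelled. With 169 per arm, a screen at 0.05/3 gives 29%, 1.64 and 52%.

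**The case against.** The strongest reply is about size. The constructs listed, such as perceived need, motivation and perceived barriers, are plausibly correlated, and correlation roughly halves the leakage at 0.20 SD. The only planning effect in the documents is 0.35 SD, set for outcomes and not mediators; at that size the leakage is 5% or less. The bias is also small beside sampling error and would seldom change a significance statement about the direct effect. All of this stands. It limits the size but does not remove the bias, since nothing in the plan assures mediator effects of 0.35 SD or more.

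It might also be said that theory governs the model, since "ultimately, however, deletion or inclusion of paths will be informed by theoretical underpinnings". That clause belongs to the later step on Lagrange Multiplier and Wald tests and does not lift the entry condition.

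Three stronger readings are tempting, and the documents do not support them:

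- A reader might infer that every retained path is exaggerated. Only the intervention-to-mediator path is inflated in all settings. The plan's announced comparison is of mediators with behaviour change, and that path is inflated only if mediators are correlated. Summed over mediators, the indirect effect is understated.
- A reader might infer that a third to a half of the mediated effect is generally lost to the direct path. That needs effects of about 0.15–0.20 SD and uncorrelated mediators, neither of which is stated.
- A reader might add that the screen lacks multiplicity control. The Aim 1 text says "all hypothesis tests will be conducted under the control of familywise error rate no greater than 0.05 level"; whether that reaches the screen is arguable, and a stricter level would worsen the bias (52% against 33% at 0.20 SD).

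**Conclusion.** The concern holds, at a limited and conditional size. The entry rule is explicit, uses the trial's own data, and is not offset elsewhere. It biases the Aim 2 decomposition: retained intervention-to-mediator paths come out too large, and dropped mediators are reported as direct effect or, when mediators are correlated, absorbed into the paths of those retained. The bias is material for mediator effects of about 0.15–0.30 SD, small at 0.35 and negligible at 0.50. With no true mediator effects, the screen does not bias the direct effect.

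The figures rest on the assumed number, strength and correlation of mediators, linear models and 169 per arm; smaller relevant subsets make matters worse. The Aim 1 comparisons, their error rate and the sample size are untouched. The change is worth making because the rule brings no gain in the settings checked and is easily removed.

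**What to change.** Remove the significance condition. List in the analysis plan the youth-level mediators from the application's figure that are measured after randomisation, and fit them all. Baseline constructs should enter as covariates or moderators: the candidates include predisposing characteristics and, in the opening of the Data analysis plan, prior service use, and some of these may precede randomisation and so cannot be moved by the intervention.

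Report each indirect effect and the direct effect with bootstrap confidence intervals, whatever the significance of the intervention-to-mediator path. Keep the screened model, if at all, as a sensitivity analysis.

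The cost is a change of wording and a somewhat larger model. In the setting checked (three uncorrelated mediators at 0.20 SD) the full model was no less precise for the direct effect.
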